Project Name

Observation of MRD Detection for General Risk Stage II Colorectal Cancer
of preoperative sensitivity and postoperative positive rate

NCT ID not yet assigned

[figure not shown]
Date: February 25, 2023

1. Project approval basis and research status

Colorectal cancer is the third malignant tumor with the highest incidence rate in the world, and its mortality rate is the second ^[1]. The incidence rate and mortality of colorectal cancer in China rank the third and fifth in all malignant tumors, respectively, and the incidence rate has shown a significant upward trend in recent years ^[2].

The adjuvant treatment for colorectal cancer after surgery is currently based on postoperative pathological staging. According to the "NCCN Guidelines for Rectal Cancer 2022. V1", for rectal cancer with T3N0M0, there is also a choice between postoperative chemotherapy and observation. Similarly, the requirements for "follow-up observation" are: highly differentiated or moderately differentiated, involving <2mm of the mesorectum, without lymphatic or vascular invasion, located in the upper rectum. In China's "CSCO Guidelines for the Diagnosis and Treatment of Colorectal Cancer (2022)", for patients with pMMR (90% of colorectal cancer are pMMR patients), if they are of general risk type, adjuvant chemotherapy can be performed after surgery, and follow-up observation can also be considered. High risk factors include: T4 stage, poor histological differentiation (poorly differentiated or undifferentiated), vascular infiltration, neural infiltration, preoperative intestinal obstruction or tumor site perforation, positive or unknown surgical margin, insufficient safety distance from the surgical margin, and

less than 12 lymph nodes submitted for examination. In other words, when the patient is a colorectal cancer T3N0M0 patient without high risk factors, doctors have difficulty selecting adjuvant treatment after surgery.

Figur 1 excerpted from page REC-4 of the "NCCN Guidelines for Rectal Cancer 2022. V1"

Although the article published in the New England Journal in June 2022 has already been applied to Phase II colorectal cancer with Signature[®] MRD detection product, and has proven its role in guiding postoperative chemotherapy^[3]. However, there are still two problems: 1. There is no independent distinction between the common risk types of stage II colorectal cancer, and there is no answer to the question of the postoperative positive rate of MRD in patients with stage II colorectal cancer common risk types; 2. There are no similar studies in the Asian population.

Therefore, we designed an observational study to observe the sensitivity and postoperative positive rate of this method in patients with general risk stage II colorectal cancer, with the aim of answering the positive rate of MDR testing in patients with general risk stage II

colorectal cancer after surgery, and laying a foundation for exploring the guidance of this method for postoperative adjuvant treatment.

Reference:

[1] Bray, F., et al. (2018). "Global cancer statistics 2018: GLOBOCAN estimates of incidence and mortality worldwide for 36 cancers in 185 countries." *CA Cancer J Clin* 68(6): 394-424.

[2] Deng, Y. (2017). "Rectal Cancer in Asian vs. Western Countries: Why the Variation in Incidence?" *Curr Treat Options Oncol* 18(10): 64.

[3] Jeanne Tie, et al. "Circulating Tumor DNA Analysis Guiding Adjuvant Therapy in Stage II Colon Cancer." *N Engl J Med*, 2022 Jun 16;386(24):2261-2272.

2. Objects and contents

2.1 Objective

To observe the sensitivity of Huajian micro MRD detection in preoperative diagnosis of patients with general risk stage II colorectal cancer, and to study its positive rates at one and three months after surgery.

2.2 Contents

Preoperative venous blood and intraoperative tumor tissue samples were reserved for patients with colorectal cancer who were estimated as stage II general risk through pelvic magnetic resonance imaging. Patients with colorectal cancer who were confirmed as stage II general risk type by postoperative pathological reports began to be enrolled. To observe the sensitivity of preoperative Huajian micro MRD detection and the postoperative positive rate of this type of patients.

2.3 Research steps

1) Patients who meet the inclusion and exclusion criteria for preoperative examinations, especially pelvic magnetic resonance imaging, are enrolled.

2) Informed consent signed by patients or family members before surgery.

3) Before surgery, 20 ml of venous blood was collected, and the dedicated anticoagulant tube was provided and stored by BGI Gene

manufacturer.

4) During the operation, tissue samples, about the size of soybeans, were kept in vitro for 30 minutes, and were routinely fixed with formalin before being handed over to BGI Gene manufacturer.

5) Due to the storage by the manufacturer, the samples shall be disposed according to the sample destruction procedure after testing.

6) After the postoperative pathological report is released, the patient is evaluated as a general risk type II colorectal cancer patient, and the BGI Gene manufacturer is notified for testing.

7) Complete exon sequencing and preoperative MRD detection.

8) Peripheral blood MRD testing was performed one month and three months after surgery under the same conditions as 5).

2.4 Evaluation indicators

Key point:

Sensitivity of preoperative MRD detection (sensitivity=number of truly positive patients/pathologically diagnosed as general risk stage II colorectal cancer)

Secondary points:

Positive rate of MRD testing at 1 month after surgery

Positive rate of MRD testing at 3 months after surgery

DFS of 2-years in patients with two MRD outcomes

2.5 Follow up

- 1) Implement a unified follow-up plan: All patients will be followed up every 3 months for the first 2 years after surgery; Observation end point is PFS of 2 years. Follow up every six months from the second to fifth year after surgery; Thereafter, a follow-up visit will be conducted annually. The follow-up includes: Finger rectal examination, blood routine, biochemical routine, tumor markers, pelvic MRI, chest and abdominal CT, endoscopy, etc.
- 2) Follow up time nodes: 3, 6, 9, 12, 18, and 24 months after surgery.
- 3) Outside the time node for the return visit, a dedicated person will conduct the follow-up by phone, letter questionnaire, email, etc

Sample size estimation

2.6 Sample number estimation

According to existing literature, the positive rate of MRD detection is 85%, and the expected sensitivity is 80% $\alpha= 0.05$, $1- \beta= 0.90$, the statistical difference can be obtained by calculating 48 cases. 50 cases were planned to be enrolled.

3. Inclusion and exclusion criteria

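### The 48 cases in section 2.6 do not follow from its inputs: 85% versus 80% at alpha 0.05 and 90% power needs about 484 to 617 patients, and the planned 50 have far less than 90% power.

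*Combined protocol and SAP*

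**What the plan says.** Section 2.6 is the whole sample size justification. It takes two rates, "the positive rate of MRD detection is 85%, and the expected sensitivity is 80" (percent), adds alpha 0.05 and power 0.90, and states that "the statistical difference can be obtained by calculating 48 cases. 50 cases were planned to be enrolled". It gives no null value, test, sidedness, margin, confidence interval width or allowance for losses.

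The primary endpoint in section 2.4 is one proportion in one group: "Sensitivity of preoperative MRD detection (sensitivity=number of truly positive patients/pathologically diagnosed as general risk stage II colorectal cancer". The objective in section 2.1 is descriptive: "To observe the sensitivity of Huajian micro MRD detection in preoperative diagnosis of patients with general risk stage II colorectal cancer". Outside section 2.6 nothing describes a comparison for this endpoint. The only contrast elsewhere is the secondary endpoint of 2-year DFS by MRD result.

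Two sections bear on what the planned 50 counts. Section 2.2 says "Patients with colorectal cancer who were confirmed as stage II general risk type by postoperative pathological reports began to be enrolled", whereas step 1 of section 2.3 says "Patients who meet the inclusion and exclusion criteria for preoperative examinations, especially pelvic magnetic resonance imaging, are enrolled".

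**The concern.** Two unequal proportions, an alpha, a power and a claim of statistical difference are the ingredients of a hypothesis test. A difference of only 5 points between rates near 80% takes several hundred patients to detect with 90% power, so 48 looks about ten times too small.

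The risk lies in how the result will be read. If the observed sensitivity does not differ significantly from 85%, a reader who trusts section 2.6 could take that as a 90%-powered finding that the assay performs as in the literature. If the real power is much lower, that reading has no basis.

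**Working it through.** **Inputs, all from section 2.6.** Rates 0.85 and 0.80, so the difference is 0.05; alpha 0.05; power 0.90; 48 cases calculated and 50 planned. Sidedness and null are not given, so every combination is tried. The single-group endpoint in section 2.4 points to a one-sample test.

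**Trying to reproduce 48.** The formula is n = [z(alpha)·√(p0(1−p0)) + z(0.90)·√(p1(1−p1))]² / (p1−p0)², with z(0.90) = 1.2816, √(0.85×0.15) = 0.3571, √(0.80×0.20) = 0.4000 and (p1−p0)² = 0.0025.

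- Two-sided, null 0.85, true 0.80: (1.9600×0.3571 + 1.2816×0.4000)² / 0.0025 = 588.03, that is 589.
- Two-sided, null 0.80, true 0.85: (1.9600×0.4000 + 1.2816×0.3571)² / 0.0025 = 616.62, that is 617.
- One-sided (z = 1.6449), null 0.85, true 0.80: 483.96, that is 484.
- One-sided, null 0.80, true 0.85: 497.78, that is 498.

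Other forms do not help. The arcsine method gives 604.0 two-sided and 492.3 one-sided. The continuity correction raises the two-sided figures to about 608 and 636. A two-sample comparison needs 988 to 1,252 per group. Lowering power to 50%, one-sided, still needs 138. The figure of 48 is not reproduced.

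**Unstated inputs that come close.** A 95% CI of ±10 points around 85% gives 1.96²×0.85×0.15/0.10² = 48.98. A two-sided test with null 65% and true rate 85% gives 48.47. Both round up to 49, and each needs an input that the plan does not contain. Neither is attributed to the sponsor.

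**Power with 50 patients, against the stated 90%.**

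| Test | Null 85%, true 80% | Null 80%, true 85% |
|---|---|---|
| Two-sided, exact, equal tails | 11.2% | 11.3% |
| Two-sided, exact, minimum likelihood | 18.7% | 11.4% |
| Two-sided, normal approximation | 19.8% | 11.5% |
| One-sided, exact | 18.6% | 21.9% |
| One-sided, normal approximation | 28.0% | 19.7% |

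The exact rows vary because the test is discrete. Against 85%, the equal-tail test rejects at 36 or fewer or 48 or more positives and has an actual size of 2.7%. The minimum-likelihood test rejects at 37 or fewer or 48 or more, with size 4.4%.

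**What 50 patients could detect.** Against a null of 85%, two-sided 90% power requires a true sensitivity no higher than 64.4% (exact equal-tail), 66.5% (exact minimum-likelihood) or 66.6% (normal). That is a shortfall of about 18 to 21 points, not 5.

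**Precision with 50 patients.** The exact (Clopper-Pearson) 95% CI for 40/50 is 66.3% to 90.0%. The exact interval contains both 80% and 85% for every count from 37 positives (59.7% to 85.4%) to 45 positives (78.2% to 96.7%). The probability of a count in that range is 87.1% if the truth is 80% and 87.5% if it is 85%.

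**Fewer evaluable patients.** The plan gives no loss rate, so these are assumed cases: 36/45 gives 65.4% to 90.4%, and 32/40 gives 64.4% to 90.9%.

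**The case against.** The strongest reply is that section 2.6 never says 80% is to be tested against 85%. It calls one figure a literature positive rate and the other an expected sensitivity, and the study is observational with no decision resting on a test. On that reading 48 may be a loosely worded precision calculation. It is true that the contrast is inferred. But these are the only two rates in the section, and a statistical difference needs two values. The precision reading gives 49 rather than 48, relies on a half-width the plan does not state, and ignores both the 80% and the power; at the expected 80% the same formula gives 61.5, that is 62. If precision was intended, the power and difference claims are still wrong. The descriptive objective supports the proposed fix.

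A second objection is that the 87% figure depends on the interval method, which the plan does not name. This stands: with Wilson intervals (38 to 45 positives) the probabilities are 80% and 86%, and with Wald intervals (37 to 44) they are 84% and 77%. The conclusion is the same under all three.

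A third is that enrolment timing is partly settled, since step 6 of section 2.3 triggers testing only after pathology and section 2.4 defines the denominator by pathology. That also stands. What remains open is whether the planned 50 are counted before or after confirmation.

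**Conclusion.** The point holds and should be corrected before the plan is relied on. Under either choice of null and either sidedness, a one-sample test of the stated rates needs about ten times or more the 48 cases claimed (484 to 617). Power at 50 patients is 11% to 20% two-sided or 19% to 28% one-sided, not 90%. This assumes that 85% and 80% are the two values compared, which is the only contrast the section offers. Without that assumption it remains true that 48 cannot be derived from what is written. The number 50 is not itself unusable: it supports an estimate with an exact 95% interval about 24 points wide (90.0 − 66.3 = 23.7 at 40/50). It does not support a claim that sensitivity differs from, or equals, 85%.

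**What to change.** Preferred: delete the 0.90 power and the statistical difference claim from section 2.6 and restate it as precision, for example:

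> The primary endpoint is estimated, not tested. With 50 evaluable patients with pathology-confirmed general risk stage II disease and 40 positives (80%), the exact (Clopper-Pearson) 95% confidence interval is about 66% to 90%.

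Report the estimate with its exact interval, and make no claim of equality with or difference from 85%. State that the 50 are counted after pathology confirmation, and align section 2.2 with step 1 of section 2.3 on this.

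Alternative, if a different null value was actually used: state that null, the test and its sidedness, and give the power that 50 patients provide.

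The cost is one paragraph and no additional patients. The price is a less flattering statement, because an interval about 24 points wide replaces the 90% power.

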3.1 Inclusion criteria

- Age 18-75;
- Pathologically confirmed rectal adenocarcinoma;
- Pathological differentiation is highly or moderately differentiated;
- The pathological stage was pT3N0, that is, invasion of the proper muscular layer of the intestinal wall without lymph node metastasis;
- No new adjuvant treatment before operation
- There was no vascular infiltration and nerve infiltration in postoperative pathology;
- No preoperative intestinal obstruction or tumor site perforation;
- No postoperative pathological margin was positive or unknown;
- The distance between the pathological cutting edge and the tumor was more than 1 cm;
- Invasion of mesentery of intestinal wall $\leq 2\text{mm}$;
- More than 12 lymph nodes were submitted for examination;
- Nonlocal recurrence and distant metastasis;
- No multiple primary carcinoma of colon and rectum;
- Physical condition score PS ≤ 2 points;
- Patients and their families can understand and are willing to participate in this study and provide written informed consent.

3.2 Exclusion criteria

- Multiple intestinal carcinomatosis
- Previous history of malignant tumor,
- There are concurrent malignant tumors in the whole body except for colorectal cancer
- Colorectal cancer with preoperative anti-tumor treatment
- Pregnant or lactating women
- There are serious complications during or after operation, affecting the prognosis
- Hepatitis B or Hepatitis C antibody positive
- HIV antibody positive
- Other diseases considered by the research doctor to affect the prognosis and survival
- Other conditions that the research doctor believes are not consistent with this study.

3.3 Termination criteria

Termination of study treatment does not represent withdrawal from the study. Subjects who terminate the study must continue to complete the remaining tasks according to the protocol requirements

Research visits. The study treatment must be terminated if the subject meets any of the following criteria:

- Subjects voluntarily withdraw from the study, terminate testing, or withdraw their informed consent;

- Subjects have poor compliance and cannot be tested on time;
- The subject is missing a visit or has a pregnancy event;
- Other situations where the researcher believes it is necessary to end the research and testing.
